5.3. Randomization and Treatment Assignment

At Visit 3, eligible patients will be randomized in a 1:1 ratio to double-blind placebo or galcanezumab 300 mg (GMB300mg), respectively. To achieve marginal balance of treatment assignments for the factors of gender, average daily attack frequency (≤ 4 attacks per day, >4 attacks per day) and investigative site, randomization will be conducted with a dynamic allocation (minimization) method (Pocock and Simon 1975) with target probability of 0.8. Assignment to treatment groups will be determined by a computer-generated random sequence using an interactive web-response system (IWRS).

5.4. Endpoints

5.4.1. Efficacy Endpoint

5.4.1.1. Cluster Headache Attack Primary Endpoint

Patient-Rated Daily Electronic Patient-Reported Outcome (ePRO) Diary: Patients will be asked to record the number of cluster headache attacks in their daily ePRO diary during SP II and SP III, which is used to derive the primary efficacy endpoint. Information regarding abortive medication use, cluster headache attack duration on average, and cluster headache attack pain severity on average will also be recorded. Pain severity will be rated using a 5-point pain scale, where 0=no pain, 1=mild pain, 2=moderate pain, 3=severe pain, and 4=very severe pain (The Sumatriptan Cluster Headache Study Group 1991). Patients should record all cluster attacks regardless of attack duration.

5.4.1.2. Derived Variables for Cluster Headache Attacks

In Study CGAL, for primary measure of cluster headache attacks, the daily data for each patient (including last 7 days in the eligibility report [prerandomization diary phase], 8 weeks of daily

data during treatment) will be converted into 9 roughly 7-calendar day intervals: the baseline 7-day interval, Week 1, 2, 3, 4, 5, 6, 7, and 8. Each day, the patient may report zero, 1, or multiple cluster headache attacks. Any ePRO diary data reported beyond the protocol defined collection period will not be used for statistical analysis.

The approach to split the postbaseline data into weekly intervals is done as follows:

- Firstly, postbaseline daily data will be split into Weeks 1 to 4 versus Weeks 5 to 8 using 1st and 2nd injection date. All data \geq 1st injection date and $<$ 2nd injection date will be considered as Weeks 1 to 4; all data \geq 2nd injection date and $<$ treatment phase disposition date will be considered as Weeks 5 to 8. If 2nd injection date is missing, then all the data before treatment phase disposition date will be put into Weeks 1 to 4.
- Secondly, data within Weeks 1, 2, and 3 will be determined using calendar days. In other words, the 1st injection date will be considered as Day 1, then Days 1 to 7 will be Week 1; Days 8 to 14 will be Week 2; Days 15 to 21 will be Week 3. Week 4 will include all the data from Day 22 to the date before the 2nd injection (or before the treatment phase disposition date if second injection date is missing).
- Thirdly, if the 2nd injection date is not missing, the data within Weeks 5, 6, 7, and 8 will be determined using calendar days. In other words, the 2nd injection date will be considered as Day 1, then Days 1 to 7 will be Week 5; Days 8 to 14 will be Week 6; Days 15 to 21 will be Week 7. Week 8 will include all the data from Day 22 to the date before the treatment phase disposition date.

For each weekly interval, the following missing data imputation method will be used:

- 1) if there are less than or equal to 3 days with nonmissing answer to cluster headache attack frequency in the weekly interval; or 2) the diary compliance rate is less than or equal to 50%, then the weekly interval will be considered missing;
- Otherwise, 1) if there are greater than or equal to 4 days with nonmissing answer to cluster headache attack frequency in the weekly interval; and 2) the diary compliance rate is greater than 50%, then the average number of cluster headache attacks across the nonmissing days will be used to impute the missing days. Furthermore, the total cluster headache attack frequency during the weekly interval will be calculated as the average number of cluster headache attacks across nonmissing days times the actual number of calendar days within each weekly interval.

The same missing data imputation approach will also be applied to secondary and exploratory efficacy measures that are derived from ePRO data.

Then to estimate a weekly outcome of the total frequency for an efficacy measure from ePRO diary, the data within each week will be adjusted to a 7-day interval by multiplying $\frac{x}{7}$, where “x” is the actual number of calendar days within each weekly interval. Lastly, the change from baseline to Weeks 1, 2, 3, 4, 5, 6, 7, and 8 will be derived.

An example of missing data imputation is described below in [Table CGAL.5.1](#).

Table CGAL.5.1. Example of Missing Data Imputation Outcome

	Example 1			Example 2		
	Number of Calendar Days	Number of Days with Nonmissing Answer to Cluster Headache Attack Frequency	Missing Data Imputation	Number of Calendar Days	Number of Days with Nonmissing Answer to Cluster Headache Attack Frequency	Missing Data Imputation
Week 1	7	7	*a	7	7	*a
Week 2	7	4	*b	7	4	*b
Week 3	7	3	*c and *d	7	3	*c and *d
Week 4	13	6	*c	13	8	*b
Week 5	7	7	*a	7	7	*a
Week 6	7	7	*a	7	7	*a
Week 7	7	7	*a	7	7	*a
Week 8	5	3	*d	3	3	*d

*a No imputation.

*b The average number of cluster headache attacks across the non-missing days will be used to impute the missing days.

*c Set to missing (diary compliance $\leq 50\%$).

*d Set to missing (number of days with nonmissing answer to cluster headache attack frequency ≤ 3).

Gated secondary, other secondary, and exploratory efficacy measures will be derived for each patient for each 7-day interval as follows:

- A 30%, 50%, 75%, and 100% responder is defined as any patient who has a $\geq 30\%$, $\geq 50\%$, $\geq 75\%$, and $=100\%$ reduction in the number of cluster headache attacks in a 7-day interval relative to baseline interval. For 30%, 50%, 75%, and 100% responder definition, percentage reduction from baseline will be calculated as follows:

$$\frac{100 \times (-1) \times (\text{weekly of cluster headache attacks at week } X - \text{weekly of cluster headache attacks at baseline Interval})}{\text{weekly # of cluster headache attacks at baseline interval}}$$

- Change from baseline for the remaining cluster headache attack days:
 - Change from baseline in the cluster headache attack average weekly pain severity for the remaining cluster headache attack days will be derived at each weekly interval through Week 8. For the calculation of mean severity of cluster headache attacks, severity has 5 categories: 0=no pain, 1=mild pain, 2=moderate pain, 3=severe pain, and 4=very severe pain. The mean severity for the remaining cluster headache attack days for each interval will be calculated as follows:

$$\frac{\text{Sum of average cluster headache severity per day during the interval}}{\text{\# of days with cluster headache attack during the interval}}$$

If there is zero cluster headache attack within the weekly interval, then the mean severity of cluster headache attack for that interval will be considered not applicable hence missing at the interval for analyses purpose.

- Change from baseline in weekly total cluster headache attack duration will be calculated for each weekly interval. Average duration of cluster headache attacks during a 24-hour period was asked in the ePRO diary. Patients were instructed to round up to the next duration selection with following choices: 15 minutes, 30 minutes, 1 hour, 2 hours, 3 hours, >3 hours. If the duration is >3 hours, then 4 hours will be imputed for the calculation of the total cluster headache attack duration. The total cluster headache attack duration for each interval will be calculated as the summation of the average duration of cluster headache attack multiplied by the number of cluster headache attacks in the day during the interval. If the total duration is more than 24 hours for a day, it will be set to 24 hours.
- The proportion of patients with a 30% or greater reduction from baseline in the weekly total cluster headache attack duration will be calculated for each weekly interval.
- Change from baseline in weekly number of times of using oxygen as abortive medication at each interval will be calculated.
- Change from baseline in weekly number of times of using oral triptan, sumatriptan nasal spray or zolmitriptan nasal spray as abortive medication at each interval will be calculated.
- Change from baseline in weekly number of times of using sumatriptan Sc as abortive medication at each interval will be calculated.
- Change from baseline in weekly number of times of using acetaminophen/paracetamol or NSAIDs as abortive medication at each interval will be derived.
- Change from baseline in number of times using oxygen as abortive medication per cluster headache attack at each interval will be derived. The endpoint at each interval will be calculated as follows:

$$\frac{\text{Total number of times using of oxygen during the interval}}{\# \text{ of cluster headache attack during the interval}}$$

- Change from baseline in number of times using oral triptan, sumatriptan nasal spray, or zolmitriptan nasal spray as abortive medication per cluster headache attack at each interval will be derived. The endpoint at each interval will be calculated as follows:

$$\frac{\text{Total number of times using the specified types of triptan during the interval}}{\# \text{ of cluster headache attack during the interval}}$$

- Change from baseline in number of times using sumatriptan Sc as abortive medication per cluster headache attack at each interval will be derived.
- Change from baseline in number of times using acetaminophen/paracetamol or NSAIDs as abortive medication per cluster headache attack at each interval will be derived. The endpoint at each interval will be calculated as follows:

Total number of times using of acetaminophen/paracetamol or NSAIDs during the interval

of cluster headache attack during the interval

- Change from baseline in total weekly dose for oral triptan, sumatriptan nasal spray, and zolmitriptan nasal spray combined will be derived. Total weekly dose will be calculated as follows:

Sum of doses of oral triptan, sumatriptan nasal spray, and zolmitriptan nasal spray during the interval * 7

of nonmissing diary days during the interval

- Change from baseline in total weekly dose for sumatriptan Sc, oral triptan, sumatriptan nasal spray, and zolmitriptan nasal spray will be derived separately. Total weekly dose, respectively, will be calculated as follows:

Sum of doses of sumatriptan Sc during the interval * 7

of nonmissing diary days during the interval

Sum of doses of oral triptan during the interval * 7

of nonmissing diary days during the interval

Sum of doses of sumatriptan nasal spray during the interval * 7

of nonmissing diary days during the interval

Sum of doses of zolmitriptan nasal spray during the interval * 7

of nonmissing diary days during the interval

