Attachment 1. Protocol CGAL Study Schedule

Study Schedule, Protocol I5Q-MC-CGAL, SP I - SP III

Patient Status	Entering in active cluster period	Entering in Remission		SP III					Comments
		SP I	SP II	Treatment					
Study Phase (SP)	Screening/ Pre-Rand. Diary	Screening	Pre-Rand. Diary	3	4 (Ph. visit)	5	6 (Ph. visit)	7	Comments
Description	1 (Note: V1 and V2 procedures are combined into V1)	1	2	3	4 (Ph. visit)	5	6 (Ph. visit)	7	
Visit	Min range: SP I/II-10 to 15d	Allowable range b/w V1 and V2: 0 d to 1 yr	Min range: SPII-10 to 15d; V2 to V3-5d	3	4 (Ph. visit)	5	6 (Ph. visit)	7	Phone visits (V4 and V6) are contacts between office visits to collect any spontaneously reported AE
Visit Day									For flow of patients through SP I and SP II, please refer to the study design Section 7.1.
Month				Day 1	Day 7	Day 30	Day 37	Day 60	
Interval (days) since previous office visit						1		2	
Interval allowance (days)					7	30	7	30	The interval from V3 to V5 and the interval from V5 to V7 should be no less than 28 days .
					+/-1	+5/-2	+/-1	+5/-2	
Informed consent	X	X							Patients who have an extended period between V1 and V2 may need to be re-consented according to local regulations. Sites will be encouraged to stay in contact with patients during SP I who enter in remission.
Inclusion and exclusion criteria	X	X	X	X					
Dispense ePRO diary	X	X							
Demographics	X		X						
Med history and pre-existing conditions	X	X							

Study Schedule, Protocol I5Q-MC-CGAL, SP I - SP III

Patient Status	Entering in active cluster period	Entering in Remission		SP III Treatment					Comments
		SP I	SP II						
Study Phase (SP)	Screening/ Pre-Rand. Diary	Screening	Pre-Rand. Diary						
	1 (Note: V1 and V2 procedures are combined into V1)	1	2	3	4 (Ph. visit)	5	6 (Ph. visit)	7	
Visit									
Treatment				X		X			IP injections are to occur after all other visit procedures are completed. Following the first dose at V3 , patients will be observed for 30 min in the office
Prior cluster headache attack history	X	X							
ECG	X		X					X	All ECGs should be collected prior to blood draws and dosing. Patients must be supine for approx. 5-10 min before ECG collection and remain supine but awake during ECG collection
Physical examination	X	X	X						Must include a brief neurological exam
Caffeine use	X		X						
Tobacco use (smoking and non-smoking)	X		X						
Nicotine use	X		X						
Alcohol use	X		X						
Height	X	X	X						
Weight	X	X	X					X	

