4.3. Exploratory Objectives

To assess whether galcanezumab is superior to placebo as measured by the following:

- Mean change in the weekly number of times an abortive medication was taken from baseline for each weekly interval through Week 8 comparing galcanezumab with placebo.
- Change in percentage of times using oxygen from baseline for each weekly interval through Week 8 comparing galcanezumab with placebo.
- Change in percentage of times using triptan from baseline for each weekly interval through Week 8 comparing galcanezumab with placebo.
- Change in percentage of times of using acetaminophen/paracetamol or nonsteroidal anti-inflammatory drugs (NSAIDs) from baseline for each weekly interval through Week 8 comparing galcanezumab with placebo.
- The proportion of patients with a 75% or greater reduction in the weekly number of cluster headache attacks from baseline for each weekly interval through Week 8 comparing galcanezumab with placebo.
- The proportion of patients with a 100% reduction in the weekly number of cluster headache attacks from baseline for each weekly interval through Week 8 comparing galcanezumab with placebo.
- Mean change from baseline in the cluster headache attack average weekly pain severity (based on 5-point scale) from baseline through Week 8 comparing galcanezumab with placebo.

5. A Priori Statistical Methods

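### At Weeks 4 and 8 the exploratory 100% response is judged over more than the 7 days in its definition (8 to 9 on schedule, 7 to 14 in window), and rescaling cannot correct this

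*SAP*

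**What the plan says.** SAP 4.3 lists among the exploratory objectives "The proportion of patients with a 100% reduction in the weekly number of cluster headache attacks", for each weekly interval through Week 8. SAP 5.4.1.2 defines all four responder thresholds (30, 50, 75 and 100%) by the "reduction in the number of cluster headache attacks in a 7-day interval relative to baseline interval". A 100% responder therefore has no recorded attack in the interval.

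The same section sets the intervals. Weeks 1 to 3 and 5 to 7 are fixed blocks of seven calendar days. The other two are open-ended: "Week 4 will include all the data from Day 22 to the date before the 2nd injection", and "Week 8 will include all the data from Day 22 to the date before the treatment phase disposition date". If there is no second injection, Week 4 runs until disposition. Attachment 1 of the protocol gives a 30-day visit interval with an allowance of +5/-2 and adds: "The interval from V3 to V5 and the interval from V5 to V7 should be no less than 28 days".

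A week is set to missing "if there are less than or equal to 3 days with nonmissing answer to cluster headache attack frequency in the weekly interval", or if "the diary compliance rate is less than or equal to 50%, then the weekly interval will be considered missing". Otherwise "then the average number of cluster headache attacks across the nonmissing days will be used to impute the missing days". The SAP extends this rule to the secondary and exploratory diary measures, and then adjusts each week's total to seven days by a factor based on its number of calendar days.

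The binary response model in SAP 5.5.8.3 contains treatment, gender, week, treatment-by-week and baseline. It has no term for the number of days observed.

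**The concern.** A count can be expressed per seven days whatever the length of the window. The absence of any event cannot: it becomes harder to achieve the longer one looks. A patient whose attack rate does not change between Weeks 3 and 4 is less likely to be a 100% responder at Week 4, only because that window is longer. The reverse applies to incomplete weeks. Four zero entries and three blank days are scored as seven attack-free days.

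What is at stake is the reading of the 100% response curve. Weeks 4 and 8 can show dips that are products of the derivation, and the average across 8 weeks mixes windows of different length. The SAP allows for unequal exposure elsewhere: the negative binomial sensitivity analysis of the primary count has an offset for compliant days. Nothing equivalent protects this endpoint.

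**Working it through.** **1. The plan's own table.** The rule (missing if at most 3 days are entered, or if entered/calendar days is at most 50%) reproduces all 16 cells of Table CGAL.5.1. For example, 4 of 7 days is imputed, 3 of 7 is missing, 6 of 13 is missing and 8 of 13 is imputed. The table itself uses a 13-day Week 4.

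**2. Length of Week 4.** With the first injection on Day 1 and the second *g* days later, Week 4 runs from Day 22 to Day *g*, which is *g* − 21 days.

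| Interval *g* | Calendar days in Week 4 | Entered days that qualify |
|---|---|---|
| 28 | 7 | 4–7 |
| 30 | 9 | 5–9 |
| 35 | 14 | 8–14 |

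If Visit 5 falls on its nominal Day 30, then *g* = 29 and Week 4 has 8 days. The same arithmetic applies to Week 8 if disposition is at Visit 7; nominal Days 30 and 60 give 30 − 21 = 9 days. The deviation list in SAP Appendix 1 flags only dosing intervals outside 21–37 days, so a Week 4 of 37 − 21 = 16 days would not be flagged there.

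**3. Rescaling.** One attack in a fully entered 14-day week becomes 2.0 after multiplying by 14/7 and 0.5 after multiplying by 7/14. Zero attacks stays 0 either way. The direction of the factor does not matter here.

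**4. Chance of 100% response on *d* observed days.** The documents give no on-treatment attack rate, so the rates are assumptions. Single rate: Poisson, 0.2 attacks/day, P = exp(−0.2*d*). Mixed population: gamma-distributed rates, mean 1/day, shape 0.5, P = (1 + 2*d*)^(−0.5).

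| *d* | Single rate | Mixed |
|---|---|---|
| 4 | 0.449 | 0.333 |
| 7 | 0.247 | 0.258 |
| 8 | 0.202 | 0.243 |
| 9 | 0.165 | 0.229 |
| 14 | 0.061 | 0.186 |

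Relative drop against a 7-day week:
- At 8 days: 1 − 0.243/0.258 = 6% (mixed), 1 − 0.202/0.247 = 18% (single rate).
- At 9 days: 1 − 0.229/0.258 = 11% (mixed), 1 − 0.165/0.247 = 33% (single rate).

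**5. Range over other Poisson rates.** The relative drop is 1 − exp(−rate × extra days).

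| Attacks/week | 8 days | 9 days |
|---|---|---|
| 0.1 | 1% | 3% |
| 0.5 | 7% | 13% |
| 1 | 13% | 25% |
| 2 | 25% | 44% |

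**6. Between-arm bias from incomplete diaries.** Suppose identical true rates, 20% versus 5% incomplete weeks, and only 4 of 7 days entered in every incomplete week (the worst case that still qualifies). The bias is 0.15 × (0.333 − 0.258) = 1.1 points (mixed) or 0.15 × (0.449 − 0.247) = 3.0 points (single rate), in favour of the less complete arm.

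**The case against.** The case for leaving the plan alone has real weight. The endpoint is exploratory and outside the multiplicity control. The SAP openly calls its intervals only roughly seven days long. Visit timing should be alike in two blinded arms, and the week effect in the model absorbs a dip common to both. Diary compliance is compared by arm for every week, so differential completeness would be seen. SAP 5.5.8.1 also expects some patients to enter remission in later weeks, and for them zero is zero over any window. All of this stands and limits the importance of the point. It does not make the Week 4 and Week 8 proportions comparable with those of the other weeks.

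Three stronger readings may tempt a reader, and the documents do not support them.

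- *The same week may be judged on anything from 4 to 14 days.* Both numbers can occur, but not in one interval. The fixed weeks allow 4 to 7 entered days, and a 14-day Week 4 needs at least 8.
- *The treatment comparison is biased.* That requires completeness or visit timing to differ by arm, and nothing in the documents shows that they do.
- *Incomplete attack-free weeks should count as failures, as in SAP 5.5.8.2.* That rule is specified for patients who stop treatment before Week 3, not for a continuing patient who skips a diary day. It would also enlarge the bias: in the scenario of step 6 it becomes 0.15 × 0.258 = 3.9 points (mixed) or 0.15 × 0.247 = 3.7 points (single rate), now against the less complete arm.

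**Conclusion.** The concern holds for the exploratory 100% response. The definition says seven days; the derivation at Weeks 4 and 8 uses 8 to 9 on schedule and 7 to 14 in window, and neither the rescaling nor the model corrects a zero/non-zero outcome for that. Under the two assumed rate models, the proportion is understated by about 6% to 18% of its value at 8 days and 11% to 33% at 9. The effect is close to nil for very low attack rates and larger for higher ones. Weeks with 4 to 6 of 7 days entered err in the lenient direction.

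The damage is chiefly to the level of the rate and its course over time. Bias between arms is conditional on differential completeness or timing, and is about 1 to 3 points in a deliberately unfavourable scenario. A reader might infer that the main efficacy conclusions are exposed. They are not exposed to visit timing: the primary endpoint and the gated Week 3 response rest on fixed 7-day weeks. The change is worth making because it is cheap.

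**What to change.** In SAP 5.4.1.2, derive responder status at Week 4 from Days 22 to 28 after the first injection and at Week 8 from Days 22 to 28 after the second. Patients seen within the protocol's 28-day minimum already have these days, so no new data are needed.

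Apply this to all four thresholds. Moving only the 100% threshold would break their nesting. Take a baseline of 14 attacks a week and a 14-day Week 4 with none on Days 22–28, then 2 a day on Days 29–35. That patient would be a 100% responder, yet the full window gives 14 attacks in 14 days, or 7 a week: a 50% reduction, which fails the 75% threshold.

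Keep the existing rule for evaluable and missing weeks, and do not score incomplete attack-free weeks as failures. Add a sensitivity analysis of 100% response restricted to weeks with all 7 days entered, which shows how much the lenient imputation contributes.

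Cost: one SAP paragraph, a small derivation change and one extra table. The downside is small: diary days after Day 28 of each cycle are not used for responder status.

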9.1. Treatments Administered

This study includes 2 treatment groups: placebo or LY2951742 300 mg. Each treatment group will be administered three 1 ml SC injections, by qualified site personnel, every 30 days for a total of 2 administrations during SP III. The designated unblinded site personnel responsible for preparing LY2951742 and placebo doses should refer to the Pharmacy Binder Dosing Instructions for LY2951742 Drug Product, 75 mg, for the preparation and dosing instructions for both LY2951742 and placebo.

The investigator or his/her designee is responsible for the following:

- explaining the correct use of the investigational agent(s) to the site personnel,
- verifying that instructions are followed properly,
- maintaining accurate records of investigational product dispensing and collection, and
- returning all unused medication to Lilly or its designee at the end of the study.

Note: In some cases, sites may destroy the material if, during the investigator site selection, the evaluator has verified and documented that the site has appropriate facilities and written procedures to dispose clinical trial materials.

Possible injection sites include the abdomen, thigh, and upper arm. Buttocks may also be used, if more appropriate for SC injection than the other sites.

Patients will be instructed to contact the investigator as soon as possible if he or she has a complaint or problem with the IP so that the situation can be assessed.

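### The SAP's conversion to a 7-day count multiplies by x/7 where it needs 7/x, so Week 4 and Week 8 attack counts and response rates are miscoded whenever the interval is not 7 days

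*SAP*

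**What the plan says.** SAP 5.4.1.2 fixes the first three weeks after each injection at seven calendar days; after the first injection, "Days 1 to 7 will be Week 1; Days 8 to 14 will be Week 2; Days 15 to 21 will be Week 3". The last interval of each dosing period is left open: "Week 4 will include all the data from Day 22 to the date before the 2nd injection", and "Week 8 will include all the data from Day 22 to the date before the treatment phase disposition date".

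For an interval with enough diary entries, the total is the "average number of cluster headache attacks across nonmissing days times the actual number of calendar days within each weekly interval". The next step is the rescaling: "the data within each week will be adjusted to a 7-day interval by multiplying $\frac{x}{7", so the multiplier is x/7, with x defined as the actual calendar days in the interval. Change from baseline and percentage response are then derived from the rescaled count.

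The same section scales weekly triptan dose the other way. For subcutaneous sumatriptan the numerator is "Sum of doses of sumatriptan Sc during the interval * 7" and the denominator is the number of answered diary days.

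On timing, Protocol 9.1 plans dosing "every 30 days for a total of 2 administrations during SP III". Protocol Attachment 1 allows +5/-2 days around a 30-day interval and adds: "The interval from V3 to V5 and the interval from V5 to V7 should be no less than 28 days".

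**The concern.** To bring an x-day total to a 7-day scale one divides by x and multiplies by 7. The SAP does the reverse, so a long interval is inflated twice: once because it contains more days, and again by the adjustment meant to remove that. Baseline is always seven days, so the error does not cancel in the change from baseline.

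Mean change in weekly attack frequency, 30% response and 50% response, each for every weekly interval through Week 8, are named secondary objectives (Protocol 6.2.2, SAP 4.2.2). Their Week 4 and Week 8 values would be wrong. So would the overall eight-week comparisons in SAP 5.5.8.3, the exploratory 75% response, and the other weekly totals taken from the diary under the same rule, such as number of abortive treatments and total attack duration.

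**Working it through.** **Inputs.** m = mean attacks per answered day; x = calendar days in the interval (SAP 5.4.1.2). Dosing interval d = 30 days, window 28 to 35 (Protocol 9.1, Attachment 1).

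**Check that x is understood as the SAP means it.** The imputation flags in SAP Table CGAL.5.1 can be reproduced with x as calendar days. For a 13-day Week 4, 6/13 = 46.2% is set to missing and 8/13 = 61.5% is imputed, as the table shows. The table does not show a rescaled count.

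**Length of Weeks 4 and 8.** With the injection on Day 1, a next visit d days later falls on Day d + 1, so the last interval is Day 22 to Day d and x = d - 21.

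- d = 28 gives x = 7; d = 30 gives x = 9; d = 35 gives x = 14.
- Attachment 1 also labels Visit 5 as Day 30 with Visit 3 as Day 1. Taken literally, that is d = 29 and x = 8.
- For Week 8 the same arithmetic holds if the disposition date is the Visit 7 date (assumption).

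**Formula as written.** Total T = m·x. Rescaled value = T·x/7 = m·x²/7. Required value = 7m = T·7/x. Ratio of recorded to true = (m·x²/7)/(7m) = x²/49, which is 1 only at x = 7.

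**Consequences.** With ratio r, a true proportional reduction p is recorded as 1 - (1 - p)·r, and the true reduction needed to be recorded as 50% is 1 - 0.5/r.

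| x | r = x²/49 | Unchanged rate recorded as | True 50% reduction recorded as | True reduction needed for 50% response |
|---|---|---|---|---|
| 5 | 0.510 | 49.0% reduction | 74.5% reduction | 2.0% |
| 7 | 1.000 | no change | 50% reduction | 50% |
| 8 | 1.306 | 30.6% increase | 34.7% reduction | 61.7% |
| 9 | 1.653 | 65.3% increase | 17.3% reduction | 69.8% |
| 13 | 3.449 | 244.9% increase | 72.4% increase | 85.5% |
| 14 | 4.000 | 300% increase | 100% increase | 87.5% |

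For 30% response at x = 9, the true reduction needed is 1 - 0.7/1.653 = 57.7%.

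**Example in counts** (assumed rate of 2 attacks a day, 14 a week). At x = 9 the total is 18: ×9/7 gives 23.14, ×7/9 gives 14.0. At x = 13 the total is 26: ×13/7 gives 48.29, ×7/13 gives 14.0.

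**Other readings.** Applied to the daily mean, x/7 gives m·x/7. Applied to the raw sum over n answered days, it gives m·n·x/7. Applied to a value already on a 7-day scale, it gives m·x, the x-day total. None is 7m for general x.

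**Other text.** SAP 5.5.1.2 refers back to 5.4.1.2 and gives no factor. The negative binomial sensitivity model in SAP 5.5.11 uses the log of compliant days over 7 as its offset. That divides counts by days/7 and agrees with the dose formulas, against the sentence at issue.

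**The case against.** The best reply is that this is a slip of wording. The sentence states its aim, the dose formulas and the sensitivity offset go the right way, and writing multiply where divide was meant would produce exactly this text. The programs may already use 7/x. The point also rests on one fraction in text converted from PDF, so its orientation should be confirmed in the signed SAP. All of that is fair, and it makes the fix easy. It does not change what the rule says.

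Second, the confirmatory analyses are largely untouched. The primary endpoint uses Weeks 1 to 3, and the gated response is at Week 3, where x = 7. That stands for complete weeks. An early leaver could be miscoded only if x is cut at the disposition date. A patient leaving on Day 19 with four diary days (Days 15 to 18) and an unchanged rate would then be recorded at 16/49 = 0.327 of baseline, a 67% reduction. The SAP does not say that x is shortened in Week 3, and non-responder imputation may apply to such a patient, so this is a possibility to close off and not a demonstrated effect.

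Third, if every patient had the same x, a baseline-adjusted comparison at a single week would scale the effect and its standard error together and leave the test statistic unchanged. That is correct, but the estimate would still be wrong, the response rates would still change, and x varies between patients.

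Fourth, not everything is affected: 100% response (zero stays zero), mean severity, per-attack ratios and triptan dose are not. The affected secondary analyses are not gated and carry no multiplicity adjustment.

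**Conclusion.** The concern holds. As written, the factor is inverted and recorded counts are x²/49 times the true 7-day count. The error arises on schedule: 1.65-fold at a 30-day interval (1.31-fold if Visit 5 falls on Day 30), and up to 4-fold at the edge of the visit window. It affects Week 4 and Week 8 mean change, the 30%, 50% and 75% response rates, the other diary-based weekly totals under this rule, and the comparisons over eight weeks. The primary endpoint and gated Week 3 response are unaffected for complete weeks.

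This rests on the SAP text as published and on x being calendar days, as the SAP defines it. The documents do not show which form the analysis programs use. It should be corrected before the analysis is run: following the plan gives wrong values for named secondary endpoints, while silently programming the right factor would depart from the plan.

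**What to change.** In SAP 5.4.1.2 replace the multiplier x/7 by 7/x, or state directly that weekly frequency is 7 times the mean number of attacks per non-missing diary day. State that this form applies to every diary-based weekly total that now uses the x/7 rule; the triptan dose formulas already have the right direction. Add the rescaled count to Table CGAL.5.1 so that the direction is visible, for example for the 13-day Week 4. Say whether x in Weeks 1 to 3 and 5 to 7 is always 7 or is shortened at the disposition date. Confirm before unblinding that the derivation programs use 7/x.

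The cost is one line of SAP text, a small table addition and a program check. No new data and no design change are needed.
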